1. OBJECTIVES

1.1 Study Design

Insomnia is a common sequela of pediatric acute lymphoblastic leukemia treatment (ALL), with significant health consequences. Prior literature demonstrates that effective methods of dealing with medically disrupted sleep include¹: (1) parent education (teaching parents about sleep norms in children with cancer and setting appropriate expectations)²; (2) extinction (addressing problematic sleep onset associations)³; (3) bedtime fading (increasing sleep drive)⁴; (4) stimulus control (leaving the bed if not asleep)⁴; (5) positive routines (calming activities that cue sleep)⁵; and (6) sleep hygiene (improving sleep environment)⁶. Despite evidence that preventive interventions are effective at reducing insomnia development, this forward-thinking approach has not been taken with ALL populations.

We conducted a mixed methods study (DFCI 21-005) of 15 parents of children in active ALL maintenance therapy to elicit stakeholder perspectives on optimal sleep interventions to prevent insomnia. Parents thematically emphasized that they felt unprepared for the extent of sleep disruptions that their child would experience, and how to communicate this with their oncology team. Parents voiced a strong desire for more information to learn more about sleep in ALL patients, and to be able to access the information from home, without the need for additional medical/psychological appointments.

The information collected from these qualitative data, informed the development of a stakeholder informed program called Sleep ALL Night. The program will be comprised of a sleep action plan, coupled with a psychoeducational website that provides families with information critical to understanding their child's sleep, as well as evidence-based strategies to reduce the impact of ALL treatment on sleep.

We will conduct a single-arm pilot study to determine the acceptability and feasibility of Sleep ALL Night in a cohort of children with ALL receiving maintenance therapy on or as per Dana-Farber ALL Consortium trials. We are interested in study acceptability both prior to, and following the program period, defined as the extent to which people receiving a healthcare intervention consider it appropriate based on their anticipated and experiential response to the program.⁷ We are also interested in study feasibility, defined as the practicality of delivering the program and conducting clinical research about the program in the setting in which it will be implemented in the future. Data from this pilot study will inform a subsequent RCT to evaluate efficacy in insomnia prevention among this highly vulnerable patient population.

1.2 Primary Objectives

1. To evaluate the acceptability and feasibility of the Sleep ALL Night intervention in a single arm pilot study of N=30 pediatric patients with ALL.
 - a. Acceptability will be defined as (1) $\geq 30\%$ of eligible participants who are approached agree to participate, and (2) participants report an average score ≥ 4 ("Agree") on the Acceptability of Intervention Measure scale.⁸
 - b. Feasibility will be defined as: (1) $\geq 70\%$ of participants report reviewing the study

action plan, (2) ≥50% of participants report accessing the psychoeducational website, and (3) ≥80% of participants complete the Intervention Assessment.

2. To refine the program materials based on participant feedback.
3. To collect preliminary data assessing the impact of the program on increasing frequency of sleep health conversations during Jimmy Fund Clinic medical appointments based on electronic medical record review of clinic notes and parent survey response.

2. BACKGROUND

2.1 Study Disease(s)

Pediatric acute lymphoblastic leukemia (ALL).

3. PARTICIPANT SELECTION

Children with a diagnosis of de novo ALL receiving treatment in the Maintenance phase of therapy either on or as per DFCI 16-001 will serve as the population for study recruitment. Selection of participants from this cohort will ensure standardized chemotherapy exposures and medical management by their oncology team. We will recruit across low-risk, high-risk and very high-risk groups as dexamethasone (a chemotherapy known to impact sleep) dosing on or as per DFCI 16-001 is identical across risk groups in the maintenance phase of therapy (6 mg/m² BID administered in 5-day pulses at the start of each 3-week chemotherapy cycle). Given known disparities in disordered sleep due to low socioeconomic status and its associated adverse social determinants of health, we will utilize available data from the open sociodemographic banking protocol DFCI 19-796 and from DFCI 16-001 embedded HMH study to ensure appropriate representation of children from low socioeconomic status homes. Annually, ~50 children are diagnosed with de novo ALL at DFCI, of whom 30% live in low-SES households, and we plan to recruit a population representative of these local data. Patients in the maintenance phase of therapy will be recruited for study participation as per the below outlined eligibility criteria.

3.1 Eligibility Criteria

Eligibility will be determined as follows:

1. Patient in the Maintenance Phase of therapy on or as per DFCI 16-001 and has completed at least two cycles of maintenance therapy to allow adequate recovery from the more intensive Consolidation phase.
2. English or Spanish speaking child and primary caregiver (parent/guardian).
3. Child aged 4-12 years.

3.2 Exclusion Criteria

1. Primary team declines permission to approach.
2. Children with critical illness (defined as ICU admission)

3.3 Inclusion of Children and Minorities

Both male and female children of all races and ethnic groups are eligible for this study. This study focuses on children with ALL with their parents as survey informants. Surveys are

available in both English and Spanish. This study will enroll racial and ethnic minorities in a manner that is reflective of the proportion of racial and ethnic minorities diagnosed with childhood ALL at DFCI. This study does not focus on any race, ethnicity, or sex. No potential research subjects will be excluded from enrollment based on race, ethnic origin, or sex; nor will any race, ethnicity or sex be preferentially enrolled. All children and their families receiving chemotherapy on or as per DFCI 16-001 who meet the inclusion criteria will be considered eligible for participation.

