the website, families will be provided with comprehensive information on how to successfully navigate the many potential disruptors of their child's sleep as they complete maintenance therapy. Feedback will be solicited through an Intervention survey (administered at Week-3) focused on the acceptability and feasibility of the intervention materials and delivery format for a family of a child with cancer. These materials are based on the American Academy of Sleep Medicine's clinical guidelines for managing disordered sleep, and child and family feedback that was provided during Phase 1 of this project. Data collection will occur over 3 months via the intervention website and during the intervention survey (administered at Week-3). To maximize data collection, families will preferably complete the intervention survey (administered at Week-3) in-person via REDCap or paper/pencil. However, surveys may also be completed using alternative methods, including, but not limited to, REDCap link texted/mailed to participants and phone/Zoom administration (read aloud by site personnel with answers recorded). Reminders to complete the survey will be sent as needed via various methods, including, but not limited to, emails, phone calls, and text messages. An Amazon gift card will also be sent to families as modest remuneration for their time completing the survey.

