11.5 Analysis of Primary Endpoints

Patient sociodemographic, disease, and treatment characteristics will be analyzed with descriptive statistics.

Primary study outcomes of acceptability and feasibility will be assessed based on the Implementation Outcomes Framework and best practice metrics for clinical trials.^{19,20} The study will be deemed acceptable if: (1) $\geq 30\%$ of eligible participants who are approached agree to participate, and (2) participants report an average score ≥ 4 (“Agree”) on the Acceptability of Intervention Measure scale. The study will be deemed feasible if: (1) $\geq 70\%$ of participants report reviewing the study action plan, (2) $\geq 50\%$ of participants report accessing the psychoeducational website, and (3) $\geq 80\%$ of participants complete the Intervention Assessment.

Primary study outcomes (Self-efficacy for Sleep and Patient-Reported Outcomes Measurement Information System Sleep Disturbance and Sleep-Related Impairment total scores; proportion of routine visits with a discussion of sleep pre/post ONN baseline visit) will be presented descriptively.

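### Parents from the formative study DFCI 21-005 are neither excluded nor flagged, so any still eligible could count toward the five acceptability and feasibility criteria and plausibly push them upward

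*Combined protocol and SAP*

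**What the plan says.** Section 1.1 describes the formative work: "We conducted a mixed methods study (DFCI 21-005) of 15 parents of children in active ALL maintenance therapy". Its results "informed the development of a stakeholder informed program called Sleep ALL Night". The same section gives the main theme, in a sentence that ends by naming the home as the place of access: "Parents voiced a strong desire for more information to learn more about sleep in ALL patients, and to be able to access the information from". Section 5.1 adds that the materials rest partly on "child and family feedback that was provided during Phase 1 of this project", without stating that Phase 1 is DFCI 21-005.

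The pilot's eligibility rules are short. Section 3.1 requires Maintenance on or as per DFCI 16-001 with at least two cycles completed, an English- or Spanish-speaking child and caregiver, and age 4-12. It sets no maximum number of cycles. Section 3.2 has two exclusions: "Primary team declines permission to approach", and critical illness. Section 3.3 then states: "All children and their families receiving chemotherapy on or as per DFCI 16-001 who meet the inclusion criteria will be considered eligible for participation".

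Sections 3.5 and 5.2 identify families from the 16-001 database and the clinical tracking system. Neither mentions a check against 21-005. Section 3.6 speaks of enrolling within a particular stretch of maintenance and of having little time to find families, but no section says where that stretch ends.

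Section 11.5 judges the pilot on five cut-offs: at least 30% of approached eligible families agree; "participants report an average score ≥ 4 (“Agree”) on the Acceptability of Intervention Measure scale"; at least 70% report reviewing the action plan; at least 50% report accessing the website; and at least 80% complete the Intervention Assessment. No section reports or analyses 21-005 families separately.

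**The concern.** The formative study and the pilot draw on the same kind of family, at a center that section 3 says sees about 50 new ALL diagnoses a year. A parent who gave views in 21-005 had already joined a sleep study run by this group and belonged to a group that asked for home-accessible sleep information. Such a parent is plausibly more likely than a new family to agree to take part, rate the program well, look at the plan and website, and return the survey. All five criteria would then move in the same direction.

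Sections 1.1 and 11.2 say the pilot will inform a later trial, and section 3.4 wants the sample to be generalizable. Uptake and use figures that include formative-study parents would describe new families less well. Feedback for Objective 2 would also come partly from people whose views fed into the program. With 30 families and cut-offs applied to point estimates, a handful of families can decide whether a bar is met.

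**Working it through.** **The plan's own figure.** The only derived design figure is the recruitment rate in section 11.2: 30 / 12 = 2.5 families per month, which agrees with the stated figure of about 3 after rounding. It does not bear on this point. The plan gives no null rate, error rate or interval for any criterion.

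**Inputs from the documents.** N = 30 (sections 1.2, 3.4, 11.2). The feasibility cut-offs in section 11.5 give these counts:
- action plan: 0.70 × 30 = 21
- website: 0.50 × 30 = 15
- completion: 0.80 × 30 = 24

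**Assumptions, because the documents give no figures.** All 30 families are in each denominator. k of them are former 21-005 families, each counting as a success with probability q = 0.90 or 1.00. The other 30 − k succeed independently at a true rate p that is 10 points below the bar. A false pass means meeting the bar in that situation.

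**Formula.** P(false pass) = P[Bin(30 − k, p) + Bin(k, q) ≥ c], where c is the required count.

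| Bar (c, p) | k = 0 | k = 1, q = 0.90 / 1.00 | k = 2, q = 0.90 / 1.00 | k = 3, q = 0.90 / 1.00 |
|---|---|---|---|---|
| Website (15, 0.40) | 17.5% | 22.4% / 23.4% | 28.2% / 30.5% | 34.7% / 38.7% |
| Action plan (21, 0.60) | 17.6% | 20.5% / 21.5% | 23.7% / 25.9% | 27.2% / 30.9% |
| Completion (24, 0.70) | 16.0% | 17.9% / 18.8% | 19.9% / 22.0% | 22.2% / 25.6% |

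**All three feasibility bars.** Section 11.5 calls the study feasible only if all three are met. If they are independent, multiply:
- k = 0: 0.176 × 0.175 × 0.160 ≈ 0.5%
- k = 3, q = 0.90: 0.272 × 0.347 × 0.222 ≈ 2.1%
- k = 3, q = 1.00: 0.309 × 0.387 × 0.256 ≈ 3.1%

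The three responses come from the same families, so they are probably positively related. The joint chance would then be above the product, but it cannot exceed the smallest single-bar figure.

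**Uptake.** The number approached is not given. Assume 100, so 30 must agree. With the others at a true 25% and former families at 90%, the false-pass chance is 15.0% for k = 0 and 27.2% for k = 3.

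**AIM mean.** Assume a true mean of 3.8 for the others, 4.5 for former families, SD 0.8, and a normal approximation. With k = 3 the expected mean is (27 × 3.8 + 3 × 4.5) / 30 = 3.87 and the standard error is 0.8 / √30 = 0.146. The chance of reaching 4 is 18.7%, against 8.6% with k = 0.

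**What is not known.** k is not given. Nor are the dates of 21-005, the ages or treatment protocol of the 15 children, or the length of maintenance. With k = 0 every figure stays in its first column.

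**The case against.** The strongest reply is that overlap may be nil. The 15 children were already in maintenance when 21-005 was done, and the program had to be developed afterwards. To be eligible now, a child must still be in Maintenance on or as per 16-001 and be aged 4-12. Section 3.6 points to a limited enrollment period. This stands as a reason to expect few such families. It is not a safeguard, because the period has no stated end and section 3.1 sets no upper limit.

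A reader might infer that these parents co-designed the program and were known to want it. Section 1.1 does not support that. It reports themes across a group, about sleep information in general, before the program existed. It does not say that each parent held each view, or that any of them saw the action plan or website. A reader might also infer that the cut-offs are reserved for families with no earlier contact. No section says so, and a 21-005 parent could still be meeting the finished program for the first time.

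The success rates of 90-100% are assumed. Former contributors could be more critical, or have less need of the website. The direction is plausible but not certain.

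Finally, the single-bar chances are already 16-18% with no overlap, which comes from applying bare cut-offs to 30 families. Overlap adds to that weakness and is not its source. A single-bar figure approximates the overall feasibility verdict only if the other two bars are comfortably met.

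**Conclusion.** The gap is real: sections 3.1 to 3.3 let a 21-005 family enter, and nothing later separates its data. The harm is conditional, and its size cannot be settled from the documents. Under the stated assumptions, three former families would raise the single-bar false-pass chance to 35-39% for the website, 27-31% for the action plan and 22-26% for completion. A wrong overall feasibility verdict would remain at about 2-3% if the bars are independent.

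Two stronger conclusions are not supported: that such families have been or will be enrolled, and that the pilot's overall result is likely to be wrong because of them. This is an inexpensive improvement to a pilot meant to inform a later trial. It does not show that the design fails.

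**What to change.** Check each screened family against the 21-005 participant list before approach. Then take one of two routes:

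- **Exclude.** Add participation in DFCI 21-005 to section 3.2 as a third exclusion.
- **Record and separate.** Allow enrollment but record prior participation. In section 11.5, judge the five criteria without these families, removing them from numerator and denominator alike (including the approached families for uptake). Report their number and the results with and without them, and keep their comments for Objective 2.

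The second route also serves if any have already been enrolled. Section 3.3 needs no rewording for either route.

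The cost is one line of text and a check against 15 families from the group's own study. The recruitment pool, or the evaluable denominator, shrinks by at most 15, and by fewer once children past Maintenance or outside ages 4-12 are set aside. If three of 30 were removed, the required counts out of 27 would be 19 for the action plan (0.70 × 27 = 18.9), 14 for the website (13.5) and 22 for completion (21.6). If the check finds no such family, nothing is lost and the report can say so.

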3.4 Planned enrollment

The overall study will enroll a total of 30 pediatric patients with ALL being treated on or as per DFCI 16-001 over 1-year. Eligible families will be offered an opportunity to consent/assent to enrollment by experienced research assistants in the hospital or clinic following permission from the primary oncology team. This strategy removes recruitment burden from busy clinical staff and has been successfully implemented in prior insomnia treatment research conducted by MPI [name]. We will recruit a patient sample representative of the racial, ethnic, and socioeconomic diversity of our patient population to ensure data from this study are generalizable. This will be operationalized by utilizing parent-reported sociodemographic data from the currently open sociodemographic banking protocol DFCI 19-796 and from the DFCI 16-001 embedded HMH study as part of our screening processes. Should COVID-19 restrictions limit in-person clinic visits during the funding period, we will implement a remote recruitment and consent strategy involving phone calls/emails after medical appointments in our center successful in previous studies by MPI [name] (NCT #03613519).

3.5 Recruitment and consent

Patients being treated on or as per DFCI 16-001 in the maintenance phase of chemotherapy who meet the above specified inclusion criteria will be identified via DFCI 16-001 study database and the Heme Malignancy clinical tracking system, which is reviewed monthly. Sociodemographic data from 16-001 and 19-796 will be used to monitor representativeness of enrolling cohort by race, ethnicity, and socioeconomic status to ensure a representative sample.

This study will follow procedures currently in place for other protocols at DFCI (e.g., 17-515, 17-402) in order to identify potentially eligible participants for recruitment purposes. These procedures have been developed in consultation with multiple disease centers and have proven to be effective and non-burdensome for clinicians and patients. Study investigators will collaborate with clinicians in the Jimmy Fund Clinic at Dana-Farber Cancer Institute in order to identify and recruit eligible participants. Recruitment materials and a study information sheet can be found in Appendix D, E and F. After getting permission to approach the subject from their oncology provider, subjects will be approached, screened for eligibility, and recruited by a member of the study staff. This may occur in-person during a hospitalization or at a scheduled clinic visit, or alternatively, via telephone, videoconference, email, or mail, as some medical visits are currently conducted as telehealth visits. These “remote” potential participants will receive the Study Information Sheet by email or mail.

Informed Consent: We are requesting a Waiver of Documentation of Informed Consent for this pilot study, as it is a minimal risk study involving procedures common in routine clinical and non-clinical practice for which signed consent is generally not required outside of the research context. All elements of informed consent will be provided verbally prior to study enrollment by study staff utilizing the Study Information Sheet (Verbal Informed Consent)) and will be provided to families.

Recruitment and Consent methods will include both in-person and remote options:

In-person:

Following provider permission to approach, eligible parents/guardians will be approached by the study staff while in clinic at DFCI or inpatient at BCH and offered an opportunity to participate following verbal informed consent. Study staff will offer discussion in a private setting (e.g., consult room) and explain details of the study including all elements of informed consent including study procedures, study risks and benefits and study goals and methods. The voluntary nature of participation will be highlighted. If, after being introduced to the study and having had the opportunity to ask questions, parent/guardians are willing to participate, they will be asked to verbally communicate their intent to participate which will be documented by study staff. Participants ages 10-12 years will provide verbal assent with the parent/guardian present, and the parent/guardian will provide verbal consent on the child's behalf. Records of all instances of verbal consent/assent, including date, will be stored in a secure study database managed by the study team. Parent/guardians will be provided with a copy of the Sleep Study Information Sheet for their reference. The patient's designated Oncology Nurse Navigator (ONN) will be informed of the consent. During the ONN's visit with the patient and guardian, the family will be provided with the sleep action plan and introduced to its use (Appendix C). The sleep action plan will be available in both English and Spanish.

Remote:

In addition to in-person recruitment, study staff may also conduct the consent process remotely. For these procedures, email addresses, mailing addresses, and phone numbers will be obtained from the patient's medical record. Eligible participants will be emailed a Sleep Study Invitation (see Appendix D) that includes the following:

- An invitation letter, that will explain the purpose and characteristics of the study and an opt out message stating they decline to participate at this time

Study staff will then follow up with a phone call after a few days to ensure that the documents have been received and gauge the family's interest in learning more. We will attempt to contact them a maximum of three times. No phone messages with the full name Dana-Farber Cancer Institute will be used. The phone call will give the parents the opportunity to opt-out or hear additional information about the study.

If the family expresses interest in participating, the study staff will provide details on the study, walk through the Sleep Study Information Sheet to ensure that all elements of informed consent are provided, and offer the family the opportunity to ask questions. If the parent and child (when applicable by age) decide to participate, they will provide verbal consent/assent in place of written documentation of informed consent. Children ages 10-12 years will provide verbal assent with the parent present, and

the parent will provide verbal consent on behalf of the child.

During the patient's next ONN visit, the family will be provided with the sleep action plan.

We request a waiver of documentation of consent/assent for parents and children based on the following considerations: (i) participating in the study constitutes "no more than minimal risk"; (ii) the rights and welfare of the subjects will not be adversely affected, since parents and children will be given all elements of informed consent both in writing and verbally; (iii) increased study feasibility: we would like to minimize the burden that may result from signing a consent form.

